### 5.5.2 Compliance with study treatment

Randomized treatment compliance is defined separately for the DB, SB aprocitentan and DB-WD parts as:

$$\text{Compliance} = \frac{[(\text{number of tablets dispensed} - \text{number of tablets returned}^*) / \text{treatment duration [days]}]}{1}$$

\* If a subject did not return his/her bottle (e.g., the bottle is lost), the compliance will not be calculated and the compliance for the parts will be set to missing. The bottle is allocated to the study part in which it was dispensed.

Here the number of tablets is calculated separately for the DB (SB aprocitentan, DB-WD, respectively) part based on the **Study Treatment Dispensing & Accountability** eCRF and the DB (SB aprocitentan, DB-WD, respectively) treatment duration is defined as in Section 5.5.1.

RI treatment compliance is defined as the number of tablets taken during the RI period according to the **Study Treatment Dispensing & Accountability** eCRF, divided by the RI treatment duration (in days) defined in Section 5.5.1.

Standardized background antihypertensive therapy compliance is defined similarly based on the **Standardized Background Antihypertensive Therapy Dispensing & Accountability** eCRF.

Randomized treatment compliance will be summarized by study part and treatment group (within study part) in the SAF, rSAF and mSAF, respectively. RI treatment compliance will be summarized based on the RIS.

Compliance to the standardized antihypertensive background therapy will be summarized by study part and treatment group (within study part) in the SAF, rSAF and mSAF, respectively.

*Adherence* (Y/N) to the standardized background antihypertensive therapy (as measured by urinalysis for valsartan) will be summarized by study part, visit and treatment group (both within study part) in the SAF, rSAF and mSAF, respectively.

A subject is considered to have interrupted study treatment or standardized background antihypertensive therapy if on the **Study Treatment Log or Background Therapy Log** the ‘Reason for treatment stop’ is ‘Interruption due to an AE’ or ‘Interruption not due to an AE’.

Reasons for study treatment interruption will be summarized by study part and treatment group (within study part) in the SAF, rSAF or mSAF, where appropriate.

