-  All AEs and SAEs that occur after signing the informed consent form and up to 30 days after study treatment discontinuation must be reported.
-  Switch to the standardized background antihypertensive therapy. Visit 1.1 may be at the same day as Visit 1. Additional visits may be performed for further assessments (e.g., to adjust the dose of the standardized background antihypertensive therapy, taking urine samples to monitor adherence).
-  Run-in eligibility criteria.
-  From this time point onwards the dose of the standardized background antihypertensive therapy must be kept stable.
-  Randomization eligibility criteria.
-  For subjects who permanently discontinue prior to Randomization due to any reason or do not fulfill the randomization eligibility criteria, these tests are not mandatory.
-  Two samples will be drawn: one sample for the central laboratory and one sample for the local laboratory to measure hemoglobin, creatinine (to determine eGFR), AST/ALT, and a pregnancy test to confirm eligibility of subjects for randomization.

ABPM = ambulatory blood pressure monitoring; AE = adverse event; ALT = alanine aminotransferase; AOBPM = automated office blood pressure measurement; AST = aspartate aminotransferase; BP = blood pressure; ECG = electrocardiogram; eGFR = estimated glomerular filtration rate; HR = heart rate;; RHT = resistant hypertension; SAE = serious adverse event; UACR = urine albumin-to-creatinine ratio.

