#### 4.1.6 Per-protocol analysis set

The PPS includes all subjects from the FAS without protocol deviations that potentially affect the primary endpoint. Reasons for exclusion from the PPS are:

- DB treatment duration less than 21 days.
- Use of at least one medication as per protocol deviation list code 04A04 and 04A07 or use of additional diuretic or rescue medication in DB part.
- Compliance with DB treatment < 80% or > 120% [as calculated in Section 5.5.2].
- Compliance with standardized background antihypertensive therapy in DB part < 80% or > 120% [as calculated in Section 5.5.2].

The purpose of the PPS is to enable a supportive analysis of the DB part.

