## 5.5 Study treatment duration and compliance

### 5.5.1 Treatment duration

Randomized treatment duration (in days) is defined separately for the DB, SB aprocitentan and DB-WD parts as the date of the last dose of treatment in the DB (SB aprocitentan, DB-WD, respectively) part minus the date of the first dose in the DB (SB aprocitentan, DB-WD, respectively) part plus one day, ignoring treatment interruptions. The detailed derivations based on the **Study Treatment Log** are given in Section 10.1.1. Randomized treatment duration will also be expressed in weeks.

RI treatment duration is defined as the date of the last dose of SB placebo minus the date of the first dose of SB placebo plus one day [see Section 10.1.1].

Standardized background antihypertensive therapy duration in the RI period as well as in the DB, SB aprocitentan, and DB-WD parts is defined similarly based on the **Standardized Background Antihypertensive Therapy Log**.

Treatment duration (in days as well as weeks) will be summarized by study part and treatment group (within study part) in the SAF, rSAF and mSAF, respectively. Total exposure (in subject-years, where a year equals 365.25 days) will also be summarized by study part and treatment group.

Time from first dose of DB treatment to (premature) treatment discontinuation in the DB or SB aprocitentan part will be summarized by treatment group using Kaplan-Meier plots (supplemented with a table displaying the numbers of subjects at risk, with an event, and censored by treatment group, using weekly intervals) in the SAF. For subjects who completed the treatment, time to discontinuation will be censored at the last dose of SB treatment (or at the last dose of DB treatment if the subject did not enter the SB part). Additionally, a ‘two-step’ Cox model with a factor for treatment in the DB part will be fitted. This model allows for different treatment effects in the DB and SB aprocitentan parts. The treatment effect in the latter part (if any) is expected to be smaller than in the former part [for details, see Section 8.2].

Time from first dose of DB-WD treatment to (premature) treatment discontinuation in the DB-WD part will be summarized similarly in the mSAF, except that the Cox model is the conventional one.

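### On its natural reading, the background-therapy compliance criterion for the PPS and mPPS does not exclude subjects who permanently stop background therapy early while continuing study treatment

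*SAP*

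**What the plan says.** SAP Section 4.1.6 lists the reasons for exclusion from the PPS. Two matter most here. For study treatment there is a minimum duration: "DB treatment duration less than 21 days". For background therapy there is a compliance range: "Compliance with standardized background antihypertensive therapy in DB part < 80% or > 120% [as calculated in Section 5.5.2". Section 4.1.7 repeats both for the DB-WD part and the mPPS.

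Section 5.5.2 defines compliance with randomized treatment as tablets dispensed minus tablets returned, divided by treatment duration in days. For the denominator it says that "treatment duration is defined as in Section 5.5.1". Run-in compliance likewise uses the run-in treatment's own duration. For background therapy the section says only: "Standardized background antihypertensive therapy compliance is defined similarly based on the" background-therapy dispensing and accountability form.

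Section 5.5.1 defines randomized treatment duration in each part as last dose date minus first dose date plus one day, with interruptions disregarded. It then adds: "Standardized background antihypertensive therapy duration in the RI period as well as in the DB, SB aprocitentan, and DB-WD parts is defined similarly", using the background-therapy log.

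**The concern.** The PPS is meant to leave out subjects whose deviations could affect the primary endpoint. The trial asks what aprocitentan does on top of a stable three-drug background, and Table 1 (footnote 14) says of the run-in onwards: "From this time point onwards the dose of the standardized background antihypertensive therapy must be kept stable". Losing that background before Week 4, or before Week 40 in the DB-WD part, is the kind of deviation the compliance criterion should catch.

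A ratio of tablets to time on the same therapy measures how well a subject took the tablets while on it. It carries no information about how much of the study part was covered. For study treatment, the SAP fills that gap with the 21-day reason. For background therapy, neither Section 4.1.6 nor Section 4.1.7 has a counterpart. At stake is whether the supportive per-protocol analyses contain the population they claim to.

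**Working it through.** The SAP gives no figure to reproduce on this point, so the check applies the rule to constructed cases.

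**Inputs**
- DB part: 4 weeks = 28 days (SAP Section 2.1).
- Exclusion limits: below 80% or above 120% (Sections 4.1.6 and 4.1.7).
- Background-therapy duration: last dose − first dose + 1 (Section 5.5.1, by analogy).
- Assumptions: one tablet a day, as the formula implies; all bottles returned; every tablet taken until the stop.

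**Formulas**
- Natural reading: tablets taken / background-therapy duration.
- Comparison: tablets taken / 28.

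| Permanent stop after Day | Natural reading | Criterion excludes? | Share of 28-day part |
|---|---|---|---|
| 7 | 7/7 = 100% | no | 7/28 = 25.0% |
| 14 | 14/14 = 100% | no | 14/28 = 50.0% |
| 20 | 20/20 = 100% | no | 20/28 = 71.4% |
| 21 | 21/21 = 100% | no | 21/28 = 75.0% |
| 22 | 22/22 = 100% | no | 22/28 = 78.6% |
| 23 | 23/23 = 100% | no | 23/28 = 82.1% |

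Imperfect pill-taking does not change the pattern. At 90% intake until a stop after Day 7, the score is 0.9 × 7/7 = 90%, against 0.9 × 7/28 = 22.5% of the part.

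**Temporary gap.** A subject off background therapy on Days 8–21 who resumes to Day 28 takes 7 + 7 = 14 tablets. Because interruptions are disregarded, the duration is 28 − 1 + 1 = 28 days. The score is 14/28 = 50%, so the subject is excluded. A subject at a steady 78% throughout is excluded as well. The rule therefore removes a 14-day gap and keeps a 21-day one (Days 8–28), because the second subject never resumed.

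**Other listed reasons**
- The 21-day reason concerns DB (or DB-WD) study treatment, which this subject continues.
- The medication reason, "Use of at least one medication as per protocol deviation list code 04A04 and 04A07 or use of additional diuretic or rescue medication in DB", is triggered by taking something, not by stopping background therapy.
- Urine valsartan adherence is summarized in Section 5.5.2 but does not determine PPS or mPPS membership.

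**Would a full-part denominator serve instead?** For the DB part it would exclude stops up to Day 22 (78.6%) and keep a stop after Day 23 (82.1%). For the DB-WD part of 12 weeks = 84 days, 80% is 0.8 × 84 = 67.2 days, so any stop up to Day 67 would be excluded. The Week 40 target in Table 6 is WD Day 28. Subjects with full background cover through the endpoint visit would be dropped for stopping afterwards.

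**The case against.** Four points have force.

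1. **The denominator is inferred.** Section 5.5.2 names a duration for randomized and run-in treatment but none for background therapy. A reader might infer that the SAP expressly divides by time on background therapy; it does not, and study-treatment duration is not ruled out. Own-therapy duration remains the natural reading, because the other two formulas each use their own treatment's duration and Section 5.5.1 defines one for background therapy. Either way, the text needs to say which is meant.

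2. **Retention is conditional.** A reader might infer that every early stopper stays in. That holds only with at least 21 days of study treatment, study-treatment compliance of 80–120%, and no listed medication, additional diuretic or rescue. Someone switched to another antihypertensive might fall under codes 04A04 or 04A07. The code list is not reproduced in the documents, so this cannot be settled.

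3. **The analyses are supportive.** All three hypotheses are tested in the FAS or mFAS under a treatment policy strategy, and no alpha depends on the PPS or mPPS.

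4. **Early stops would be visible elsewhere.** Background-therapy duration, urine valsartan adherence and protocol deviations are all summarized by group (Sections 5.5.1, 5.5.2 and 5.2). These would show an imbalance between arms but would not correct the membership of the PPS or mPPS.

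It could also be said that such stops will be rare. The documents do contemplate them: SAP Section 7.1.1.5 refers to adverse events leading to discontinuation of background therapy, and Section 2.1.2 of the protocol addendum asks sites to guard against gaps in its supply. They give no frequency.

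**Conclusion.** The point stands as a correction that should be made, limited to the supportive PPS and mPPS analyses. On the natural reading, the criterion gives about 100% to a subject who permanently stops background therapy at any time while continuing study treatment, and it excludes lesser deviations. A stop after Day 7 scores 100% for 25% coverage of the DB part; a 14-day gap with resumption scores 50% and is removed. The conclusion rests on the own-duration denominator and on no other exclusion reason applying.

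A reader might go further and infer a bias of some size in the treatment effect. The documents do not support that. They give neither the number of such stops, nor their split between arms, nor the blood pressure change that follows. The direction is also open: if stops occurred mainly for low blood pressure on active treatment, keeping those subjects would tend to shrink the per-protocol effect. The primary and key secondary tests are unaffected.

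**What to change.** 1. Add to Sections 4.1.6 and 4.1.7 a reason parallel to the existing one: background-therapy duration in the DB (respectively DB-WD) part of less than 21 days, taken from the background-therapy log. In the cases above it would exclude permanent stops up to Day 20 and keep later ones, the same tolerance the SAP allows for study treatment.
2. Name the background-therapy denominator in Section 5.5.2. Do not use the full 12-week DB-WD duration for the mPPS, because it would exclude subjects who stop only after Week 40. Changing the denominator and adding the 21-day reason are not interchangeable: a stop after Day 21 or 22 of a 28-day part is excluded by the first and kept by the second.
3. As a secondary matter, state how missing compliance bears on PPS and mPPS membership, for study treatment and background therapy alike. Section 5.5.2 sets compliance to missing when a bottle is not returned. A missing value is neither below 80% nor above 120%, and the SAP does not say whether the subject stays in.

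The cost is a few lines of SAP text. Background-therapy duration by part is already a planned derivation and the log data are collected. The downside is that the PPS and mPPS may lose a few subjects.

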## 6 EFFICACY VARIABLES AND ANALYSES

### 6.1 Overall testing strategy

Three null hypotheses will be tested in this study. The first two null hypotheses ( $H_{10}$  and  $H_{20}$ ) will be tested in parallel using the Bonferroni correction. The third null hypothesis ( $H_{30}$ ) will only be tested if  $H_{10}$  or  $H_{20}$  is rejected.

The first null hypothesis  $H_{10}$  is that there is no difference between aprocitentan 25 mg and placebo in the DB part in the mean change from baseline to Week 4 in mean trough SiSBP. The alternative hypothesis  $H_{1a}$  is that there is a difference between these groups:

$$H_{10}: \mu_1 = \mu_0 \quad \text{vs} \quad H_{1a}: \mu_1 \neq \mu_0.$$

Here  $\mu_0$  and  $\mu_1$  denote the mean change from baseline to Week 4 in mean trough SiSBP in the placebo and aprocitentan 25 mg groups, respectively. This hypothesis will be tested at a two-sided significance level of 0.025.

The second null hypothesis  $H_{20}$  is that there is no difference between aprocitentan 12.5 mg and placebo in the DB part in the mean change from baseline to Week 4 in mean trough SiSBP. The alternative hypothesis  $H_{2a}$  is that there is a difference between these groups:

$$H_{20}: \mu_2 = \mu_0 \quad \text{vs} \quad H_{2a}: \mu_2 \neq \mu_0.$$

Here  $\mu_0$  and  $\mu_2$  denote the mean change from baseline to Week 4 in mean trough SiSBP in the placebo and aprocitentan 12.5 mg groups, respectively. This hypothesis will be tested at a two-sided significance level of 0.025.

The third null hypothesis  $H_{30}$  is that there is no difference between aprocitentan 25 mg and placebo in the DB-WD part in the mean change from DB-WD baseline (Week 36) to Week 40 in mean trough SiSBP. The alternative hypothesis  $H_{3a}$  is that there is a difference between these groups:

[figure not shown]
$$H_{30}: v_1 = v_0 \quad \text{vs} \quad H_{3a}: v_1 \neq v_0.$$

Here  $v_0$  and  $v_1$  denote the mean change from DB-WD baseline (Week 36) to Week 40 in mean trough SiSBP in the placebo and aprocitentan 25 mg groups, respectively. This hypothesis will only be tested if  $H_{10}$  or  $H_{20}$  is rejected: at a two-sided significance level of

0.05 if both  $H_{10}$  and  $H_{20}$  have been rejected and at a two-sided significance level of 0.025 if only one of  $H_{10}$  and  $H_{20}$  has been rejected. The overall type I error is protected at 0.05 [Bretz 2009].

The testing strategy is summarized in Figure 2.

**Figure 2 Testing strategy**

The '1' next to the arrows indicates that if  $H_{10}$  ( $H_{20}$ ) is rejected the associated alpha of 0.025 will be propagated to test  $H_{30}$ .

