# 3 OBJECTIVES

## 3.1 Primary objective

The primary objective of the study is to demonstrate the BP lowering effect of aprocitentan when added to standard-of-care in subjects with true RHT.

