#### 4.1.5 Modified Full analysis set

The mFAS includes all subjects from the FAS who were re-randomized in the DB-WD part of the study and who have a DB-WD baseline SiSBP, measured by AOBPM at trough. Subjects will be evaluated according to their assigned study treatment in the DB-WD part: aprocitentan 25 mg or placebo.

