### 6.2.3 Main analysis for the primary endpoint

The main analysis of the change from baseline to Week 4 (i.e., in the DB part) in mean trough SiSBP measured by AOBPM will be conducted on the FAS. The treatment groups in this analysis are aprocitentan 25 mg, aprocitentan 12.5 mg, and placebo. The first and second null hypotheses ( $H_{10}$  and  $H_{20}$ ) will be tested as described in Section 6.1.

Changes from baseline to post-baseline visits up to Week 4 in mean trough SiSBP will be analyzed using a mixed model with factors for treatment group, visit and treatment by visit interaction, and covariates for baseline SiSBP and the interaction between baseline SiSBP and visit. An unstructured covariance matrix will be used to account for the correlation between repeated BP measurements from the same subject.

LSM differences vs placebo at Week 4 and their 97.5% CIs will be obtained from the model. The associated p-values will be used to test the first and second null hypotheses.

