#### 6.4.2 Analyses

All other secondary efficacy variables will be tested at the two-sided significance level of 0.05. No correction for multiplicity will be applied.

- *Change from baseline to Week 4 of DB treatment in mean trough SiDBP measured by AOBPM* will be analyzed in the FAS using the same mixed model as specified for SiSBP (main analysis) in the DB part.
- *Changes from baseline to Week 4 of DB treatment in 24 h mean SBP and DBP measured by ABPM* will be analyzed in the aFAS using an ANCOVA with a factor for treatment group and a covariate for baseline 24 h mean SBP (or DBP).
- *Change from DB-WD baseline (Week 36) to Week 40 of DB-WD treatment in mean trough SiDBP as measured by AOBPM* will be analyzed in the mFAS using the same mixed model as specified for SiSBP (main analysis) in the DB-WD part.
- *Changes from DB-WD baseline (Week 36) to Week 40 of DB-WD treatment in 24 h mean SBP and DBP as measured by ABPM* will be analyzed in the maFAS using the same ANCOVA as described for changes from baseline to Week 4 of DB treatment in 24 h mean SBP and DBP, but with baseline replaced by DB-WD baseline (Week 36).

The analyses of the other secondary endpoints are summarized in [Table 4](#).

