## 8.2 Analysis details

### 8.2.1 Mixed model for repeated measurements

This model is used, for example, for the main analyses of the primary and the key secondary endpoints.

Assuming the data are in ‘long’ format (i.e., one row for each subject/visit) example SAS® statements for the primary endpoint analysis are:

```
proc mixed data=db;
  class subjid trt01pn avisitn;
  model chg=trt01pn avisitn trt01pn*avisitn base base*avisitn/ ddfm=kr;
  repeated avisitn/ subject=subjid type=un;
  lsmeans trt01pn*avisitn/ diff=control ('3' '6') alpha=0.025;
run;
```

The data set *db* includes baseline SiSBP (*base*) as well as changes (*chg*) from baseline to Weeks 2 and 4. Furthermore, *trt01pn* equals 1, 2 and 3 for aprocitentan 12.5 mg, aprocitentan 25 mg and placebo in the DB part, respectively, and *avisitn* is 5 and 6 for Weeks 2 and 4, respectively. The Bonferroni correction [Section 6.1] will be applied by comparing the two-sided p-values vs 0.025 (rather than adding *adjust=bonf* to the *lsmeans* statement).

Again, assuming the data are in ‘long’ format example SAS® statements for the secondary endpoint analysis are:

```
proc mixed data=dbwd;
  class trt01pn subjid trt03pn avisitn;
  model chg=trt01pn trt03pn avisitn trt03pn*avisitn wk36 wk36*avisitn/
  ddfm=kr;
  repeated avisitn/ subject=subjid type=un;
  lsmeans trt03pn*avisitn/ diff=control ('5' '13') alpha =0.05(1);
run;
```

The data set *dbwd* includes DB-WD baseline (Week 36) SiSBP (*wk36*) as well as changes (*chg*) from DB-WD baseline (Week 36) to Weeks 38 and 40. Furthermore, *trt03pn* equals 4 and 5 for aprocitentan 25 mg and placebo in the DB-WD part, respectively, and *avisitn* is 12 and 13 for Weeks 38 and 40, respectively. Note that *trt01pn* (treatment in the DB part) is now used as a stratum.

 The alpha level needs to be adjusted to 0.025 in case one of H10 and H20 has been rejected.

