### 8.2.3 Tipping point analysis assuming missing not at random

The tipping point analysis will be performed using MI assuming a monotone missing data pattern. Any non-monotone missing data will first be imputed under MAR, as described in Section 8.2.2. Missing data will initially be imputed under MAR, but the aprocitentan groups will be 'penalized' by adding a shift of  $s$  mmHg to each imputed value. This will be done for a series of  $s$  values (henceforth, shift parameters). Only positive shift parameters will be considered since these correspond to a smaller reduction or larger increase in BP. For each shift parameter the multiple data sets are analyzed using an ANCOVA for the last time point (for the primary endpoint this is *chg4*, the change from baseline to Week 4 in SiSBP) and the results are combined using PROC MIANALYZE. This is implemented in the following SAS® macro:

```
%macro tipping (dset=, smin=, smax=, step=, seed=, out=);  
* data set &dset should be in wide format;  
  
* obtain monotone missing data pattern;  
proc mi data=&dset nimpute=250 seed=&seed out=mono;  
  var base chg2 chg4;  
  mcmc impute=monotone;  
run;  
  
proc sort;  
  by _Imputation_;  
run;  
  
data &out;  
  set _null_;  
run;  
  
ods select none;  
%do s=smin %to &smax %by &step;  
proc mi data=mono nimpute=1 seed=&seed out=tip;
```

```
by _Imputation_;
class trt01pn;
var trt01pn base chg2 chg4;
monotone regression;
mnar adjust(chg4/ shift=&s adjustobs=(trt01pn='1'));
mnar adjust(chg4/ shift=&s adjustobs=(trt01pn='2'));
run;

ods output diffs=diffs;
proc mixed data=tip;
  by _Imputation_;
  class trt01pn;
  model chg4=trt01pn base;
  lsmeans trt01pn/ diff=control('3');
run;
ods output close;

ods output parameterestimates=parmest;
proc mianalyze parms=diffs;
  class trt01pn;
  modeleffects trt01pn;
run;
ods output close;

data parmest;
  shift=&s;
  set parmest;
run;

data &out;
  set &out parmest;
run;
%end;
ods select all;
%mend tippoint;
```

An example of the associated macro call is:

```
%tippoint (dset=mono, smin=0, smax=50, step=1, seed=125160, out=tipout);
```

The p-value in data set *tipout* can be plotted vs the shift parameter. The shift parameter at which statistical significance is lost (in the DB part when the two-sided  $P > 0.025$ ) indicates

how severe departures from the MAR assumption must be to overturn the conclusions of the main analysis.

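### Does the testing strategy in SAP Section 6.1 go wrong by not returning alpha from H30 to a dose that missed 0.025?

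*SAP*

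**What the plan says.** SAP Section 6.1 sets three hypotheses. H10 (25 mg) and H20 (12.5 mg) concern the Week 4 change in trough sitting systolic pressure against placebo. For each of them, "This hypothesis will be tested at a two-sided significance level of 0.025". H30 concerns 25 mg against placebo from Week 36 to Week 40. It is tested at 0.05 if both dose nulls fall, at 0.025 if one does, and not at all otherwise. Section 6.1 states that overall type I error is held at 0.05.

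The image of Figure 2 is not available. Its caption says that if H10 or H20 "is rejected the associated alpha of 0.025 will be propagated to test" H30.

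The rest of the SAP keeps the same fixed threshold for the doses. In Section 6.2.3, "LSM differences vs placebo at Week 4 and their 97.5% CIs will be obtained from the model". In Section 8.2.1 the Bonferroni correction "will be applied by comparing the two-sided p-values vs 0.025". Section 8.2.3 uses 0.025 for the double-blind tipping point. Nothing describes alpha leaving H30. The remaining secondary endpoints stand outside the scheme: "All other secondary efficacy variables will be tested at the two-sided significance level of 0.05. No correction for multiplicity will be applied" (Section 6.4.2).

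**The concern.** Section 6.1 cites a graphical, sequentially rejective method. In such graphs a rejected hypothesis usually hands its alpha to those still open. Here H30 is a dead end: the alpha that reaches it is neither returned to an unrejected dose nor used for other secondary endpoints. A reader who knows the method will notice that the procedure is not exhaustive.

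The practical case is one dose rejected at 0.025, H30 rejected at 0.025, and the other dose at, say, p = 0.04. The plan allows no claim for that second dose, although a procedure with return arrows could claim it and still hold the familywise rate at 0.05. At stake would be the power to claim both doses.

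**Working it through.** **1. The plan's own figure.** The Bonferroni split gives 0.025 + 0.025 = 0.05. With 1:1:1 allocation the two dose statistics share the placebo arm and correlate at 0.5. Taking H30 as independent and giving non-null tests near-certain power, the familywise error (4 million draws per configuration) is:

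| True nulls | As planned | With return arrows |
|---|---|---|
| all three | 0.0465 | 0.0465 |
| both doses | 0.0465 | 0.0465 |
| one dose and H30 | 0.0495 | 0.0495 |
| H30 only | 0.0500 | 0.0500 |
| one dose only | 0.025 | 0.050 |

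The third row can be checked by hand: 0.025 + 0.975 × 0.025 = 0.0494. The stated 0.05 is confirmed. The unused alpha appears only in the last row.

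**2. What return arrows could change.** Suppose H30 passes its alpha to the unrejected dose, which is then retested at 0.025 + 0.025 = 0.05. The first rejection must still be H10 or H20 at 0.025, so the chance of at least one dose claim cannot move. The retest happens only after H30 has been rejected, so the H30 result cannot move either. Only the chance of claiming both doses can rise.

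**3. Size of that rise.** The documents supplied give no dose effect, SD or dose power, so these inputs are partly assumed:

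- Standardized effect δ, back-solved from Section 2.1 (85% power with 324 re-randomized, 1:1): (1.960 + 1.036)/√(324/4) = 0.333 if planned at alpha 0.05, or (2.241 + 1.036)/9 = 0.364 if at 0.025.
- 730 randomized (Section 2.1).
- 462 re-randomized, from 730 × 380/600 (assumption).
- The 25 mg effect at Week 4 equals δ (assumption).

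Noncentrality is δ√(N/6) per dose and δ√(n/4) for H30. For δ = 0.333 and equal doses:

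- Each dose: 0.333 × √(730/6) = 3.67; power at 0.025 is Φ(3.67 − 2.24) = 0.924. With correlation 0.5, both doses succeed with probability 0.870.
- H30: 0.333 × √(462/4) = 3.58; power at 0.025 is Φ(3.58 − 2.24) = 0.909.
- P(one dose below 0.025, the other between 0.025 and 0.05) = 0.0508.
- Gain = 0.0508 × 0.909 = 0.046, so both-dose power goes from 87.0% to 91.6%.

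For δ = 0.364 the gain is 2.9 points (93.3% to 96.1%, from unrounded values). If 12.5 mg has 75–85% of the 25 mg effect (no source), it is 5.1 to 8.5 points. With the planned 5% missing at Week 4 and 10% at Week 40, the ranges are 2.3–5.0 (equal doses) and 4.5–8.6 (weaker 12.5 mg).

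**4. Sensitivity to the main assumption.** Week 4 add-on and withdrawal after Week 36 are different contrasts, so equality of effect is only a convenience. With δ = 0.333 for H30 and equal doses, the gain is 4.6 points if the double-blind effect is the same, 1.9 if it is 15% larger and 0.5 if it is 30% larger. A smaller double-blind effect would raise it.

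**5. Where the gain comes from.** For a weaker 12.5 mg, 4.1–7.4 of the 5.1–8.5 points arise by rescuing 12.5 mg through H30. The 25 mg route alone gives 0.7–1.6 points, or 1.4–2.3 if doses are equal.

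**6. The price.** A truly ineffective dose is now rejected with probability 0.025. With return arrows this becomes 0.041 (other dose 90% power, H30 85% at 0.05) or 0.044–0.046 under the inputs in step 3, and at most 0.05.

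**The case for a change.** The best argument for change is that the alpha is already declared, the edit needs no new data, and two doses tested as separate primary hypotheses can each be lost separately. A gain of 5 to 8 points for a weaker 12.5 mg would not be trivial. A reduced version that returns alpha only to 25 mg avoids supporting one dose with data on another. At the least, the SAP could say that alpha is deliberately not returned.

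What stands is the observation that the procedure is not exhaustive, and that an exhaustive version would also be valid. The rest does not make it a fault:

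- H30 is a key secondary test of 25 mg only, in a set limited to "all subjects from the FAS who were re-randomized in the DB-WD part of the study" (Section 4.1.5). Keeping primary dose claims independent of it is a sound reason for a one-way graph.
- The objective is about the drug, not about each dose: "The primary objective of the study is to demonstrate the BP lowering effect of aprocitentan when added to standard-of-care" (Section 3.1). One rejected dose serves it and opens H30. No supplied text sets power for claiming both.
- Section 1 records that SAP Version 3 was written after all subjects had been randomized and after agencies had commented on Version 2. Relaxing a primary rejection rule then would need strong grounds. Section 11 lists no change to the testing strategy, which suggests that the main protocol, not supplied here, fixes the same one.
- The 25 mg-only version gains at most about 2 points under the inputs used.
- An added sentence would alter no result, since Sections 6.1 and 8.2.1 already fix the 0.025 threshold without ambiguity.

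**Conclusion.** The concern does not hold. Section 6.1 claims familywise control at 0.05 and achieves it; it does not claim to use all the alpha in every configuration. The change in the chance of at least one dose claim, and in the chance of rejecting H30, is exactly zero whatever effects are assumed. The possible gain in claiming both doses ranges from about 0.5 to 8.6 points over the scenarios examined. It depends mainly on the undocumented double-blind effect and dose ratio. Against it stand a higher false-rejection risk for an ineffective dose, within 0.05, and a primary claim made dependent on a secondary result. Statisticians may reasonably prefer either graph, so this is a design preference and the plan needs no correction. The reading of Figure 2 rests on its caption and the text of Section 6.1, as the image is not available.
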